High-Resistance Circuit Training. An adapted version of Alcaraz's HRC was utilized in the intervention. Exercises and intensities used by ST was the same for HRC except HRC participants performed the first three exercises as a circuit with 35 seconds rest between exercises (Figure 4).

Figure 4. Protocols for the ST and HRC Training Groups

[figure not shown]

Figure 4 shows the Traditional Strength Training (ST) and High-Resistance Circuit Training (HRC) interventions at week 4 of the intervention. ST participants performed four sets of six reps of a single exercise with 1 minute rest between sets. HRC performed the same exercises in a circuit fashion rotating from one exercise to another with 35 sec rest between sets.

Feasibility outcomes

Primary feasibility outcomes included recruitment process, sample size, consent rate, retention rate, fidelity, attendance, participant experience, and adverse events.

Recruitment process. The recruitment process refers to the protocols used to find, select, and enroll participants into a study [41]. The recruitment process for this study was represented by reporting the total number of unique QR code scans from posted flyers and tabling events, the number of completed interest forms, the number of eligible participants and the number of consented participants. A recruitment period of 3 weeks was given for the before and after-school trials.

Sample size. Sample size was used as another key feasibility marker and refers to the total number of individuals used in the intervention. A sample size of 30 participants per trial with 15 participants in each treatment group was established based on previous literature examining the difference between resistance training groups [32], suggestions of 12 participants minimum per group in feasibility trials from Julious [42], and practicality how many participants could receive intervention treatment with proper supervision. While larger sample sizes would be ideal for secondary fitness outcomes, the primary purpose of this study was to assess feasibility outcomes and not report statically powered differences.

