Consent rate. Consent rate is often referred to as the percentage of participants enrolled divided by the number of eligible participants [43]. For this study, consent rate was calculated by taking the total number of participants that consented and were randomized divided by the number of eligible students. An acceptable consent rate was set at 80% based on findings from Jacques [43].

Retention rate. Retention rate is defined as the percentage of the total number of randomized participants assessed for primary outcomes and used in the primary outcome analysis [43]. For the purpose of this study, researchers were interested in retention for both primary and secondary outcomes meaning researchers tracked retention from pre-intervention fitness testing, through treatments, and post-intervention fitness testing sessions. The follow up interview was not included in calculating the retention rate. Only participants that withdrew from the study or were not included in the primary and secondary outcome analysis influenced the retention rate. Thus, retention was calculated as the percentage of participants that completed pre and post-intervention fitness assessments and intervention treatment divided by the number of participants randomized into treatment groups. Participants that withdrew (i.e., stopped attending) from the study were tracked by the investigator. Based on prior literature, 80% retention rate was used as an acceptable threshold [44].

Fidelity. Fidelity is referred to how well an intervention was delivered as intended and is measured at the participant, deliverer or setting level [41]. For this study, fidelity was assessed at the instructor (deliverer) and participant level. Instructor fidelity was measured as a percentage by totaling the provided sessions divided by the total number of planned sessions. An acceptable percentage was set at 80% due to conflicts with events such as holiday breaks or parent teacher conferences. To assess participant fidelity, the primary researcher and participants recorded session durations, completed sets and intensity along with activity and diet audits at weeks 2, and 4 of the intervention. The activity and diet audit included a modified Copper Institute Fitnessgram and Activitygram questionnaire (Figure 5). If participants recorded additional days of aerobic, muscular strength and muscular endurance activities and/or a dramatic change in diet,

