resulting post-intervention data was excluded in the secondary performance outcomes data analysis.

Figure 5. Modified Fitnessgram Physical Activity and Diet Audit Questions

Aerobic	Outside of the intervention with the researcher, how many of the past 7 days did you participate in any physical activity for a total of 30 to 60 minutes or over the course of a day? This includes moderate to vigorous activities (walking, slow bicycling, or outdoor play) as well as vigorous activities (jogging, active games, or active sports such as basketball, tennis, or soccer). (0, 1, 2, 3, 4, 5, 6, 7 days)
Muscular strength and endurance	Outside of the intervention with the researcher. how many of the past days did you exercise to strengthen or tone your muscles? This includes exercises such as push-ups, sit-ups, or weightlifting. (0, 1, 2, 3 ,4 ,5 ,6 ,7 days)
Diet	Have you changed your diet in the past 7 days? If so, please describe.

Figure 5 is a modified physical activity and diet questionnaire from the Cooper Institute's Fitnessgram and Activitygram assessment manual to investigate additional activity and diet changes outside of the investigation [45].

Participant attendance. Participant attendance was observed by the researcher and measured as attended sessions divided by total sessions offered. Based on systematic reviews and meta-analyses [46, 47], 80% was selected as an acceptable attendance threshold.

Adverse events. Adverse events were recorded during the intervention by the participants on workout documents and by observations from the primary researcher. The primary researcher used no adverse events as an acceptable threshold.

Participant experience. Participant experience was assessed by utilizing the validated short form 4 item Physical Activity Enjoyment Scale (PACES-S) survey for adolescents [48]. Participants answered 4 items including: “I enjoyed it; I find it pleasurable; It is very pleasant; and It feels good” by responding with the five-point Likert scale ranging from 1= “strongly disagree” to 5 = “strongly agree”. To further investigators’ depth of understanding, participant experience was also assessed by a follow up interview concluding the intervention. Please see qualitative assumptions, interview process and qualitative data analysis section below for further details.

Progression criteria

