Of the above feasibility measures, selected outcomes were used as key markers to assess if further investigations were warranted for the future. The following criteria for evaluating feasibility are below:

1. No adverse events related to the intervention treatment.
2. Sample size of 30 participants per trial.
3. Consent rate no less than 80%.
4. Retention rate no less than 80%.
5. Attendance rates no less than 80%.

If all five criteria were met, then further investigations can continue without modification.

If three to four criteria were met, then further investigations can continue with modifications. If two or less criteria were met, the study is assessed as not feasible.

Secondary outcomes

All secondary outcome assessments were taken pre and post-intervention. Testing protocols required participants to avoid strenuous physical activity 48 hours prior to testing days.

Assessments took a single session to complete and all participants were tested within similar time periods.

Bioelectric Impedance Analyzer. In a separate private room, one participant at a time weighed themselves on a certified scale. Participants used the handheld Omron model HBF-306 to enter their weight, age, sex and activity level. Resulting BMI and body fat percentage data was recorded. Omron HBF-306 has been shown to be a reliable tool to track body composition over time [49].

Isometric lower body pull. Using the Baseline 12-0400 Back-Leg-Chest dynamometer participants stood up-right and feet hip width apart on the dynamometer platform with the chain adjusted so the handle was at the intra-articular space of the knee joint. Participants were instructed to grip the handle evenly at the center then produce a maximal 5 sec pull keeping the back from bending and arms straight. Participants were allowed to rest 30 sec between attempts. Participants had one practice attempt for familiarization purposes and then the best score of the three following attempts were recorded. Prior research has established reasonable test-retest reproducibility of the Baseline 12-0400 Back-Leg-Chest dynamometer in adolescent populations [50].

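### Adverse events are recorded only while participants attend training, so a training-related injury that ends attendance can be missed and the zero-event criterion still scored as met

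*Combined protocol and SAP*

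**What the plan says.** All references are to the combined protocol and SAP.

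- **Capture** (Feasibility outcomes, Adverse events): "Adverse events were recorded during the intervention by the participants on workout documents and by observations from the primary researcher". The same paragraph sets the threshold: "The primary researcher used no adverse events as an acceptable threshold".
- **Decision** (Progression criteria, item 1): "No adverse events related to the intervention treatment". Meeting all five criteria allows further work unmodified, three or four allows it with modifications, and two or fewer means not feasible.
- **Withdrawal** (Feasibility outcomes, Retention rate): "Participants that withdrew (i.e., stopped attending) from the study were tracked by the investigator". The paragraph mentions neither a reason for stopping nor any contact about harm.
- **Other contacts.** The week 2 and week 4 audits (Fidelity; Figure 5) ask about outside activity and diet only. The one-month interview is by invitation. Its guide (Figure 6) has no item on pain or injury, and nothing links its answers to the adverse-event count.
- **Supervision** (Protocol): the primary researcher supervised the training sessions, planned at three a week for four weeks.

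**The concern.** Both capture routes work while the participant is attending: an entry on a workout document, or an event that the researcher sees. The plan equates withdrawal with no longer attending. Someone whose knee or back becomes painful the day after a session, and who does not come back, produces no further workout document and is not there to be observed. The same holds for symptoms that appear after the final session, which closes the week with the highest prescribed exertion (Figure 3). In these cases the injury itself causes the record to be missing, so the gap is not random.

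The stake is the first progression criterion. Its threshold is zero, so a single missed related event changes it from failed to met. It is also the only safety criterion in a feasibility study of adolescents whose purpose is to decide whether a further trial should go ahead.

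**Working it through.** The plan gives no figure for adverse-event capture, so there is none to reproduce. Three checks follow.

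**Inputs.** Seven participants took part (Participants); I assume that these are all who were randomised. The target was 30 per trial ("A sample size of 30 participants per trial with 15 participants in each treatment group was established based on previous literature"). The rate thresholds are "Retention rate no less than 80" percent and "Attendance rates no less than 80" percent. Planned sessions: 3 × 4 = 12.

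**1. Would the other criteria reveal one injury dropout?**

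- Retention, pooled: (7 − 1)/7 = 85.7%, which passes. Two dropouts give 5/7 = 71.4%, which fails.
- Attendance, pooled, if the other six attend everything and the injured participant attends nothing: (6 × 12)/(7 × 12) = 72/84 = 85.7%, which passes. The ratio is 6/7 whatever the number of sessions.
- At the planned 30, six dropouts give 24/30 = 80.0%, which still passes.
- Scored per trial, the answer changes. The split is not given. Assuming 3 and 4, one dropout gives 2/3 = 66.7% or 3/4 = 75%, and retention fails.

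So with pooled scoring, one uncounted injury dropout can leave the adverse-event, retention and attendance criteria all scored as met.

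**2. When does the adverse-event criterion decide the result?** The sample-size criterion fails for any split of 7. Let k be the number of the three rate criteria (consent, retention, attendance) that are met. The total is then k + 1 if the adverse-event criterion is met and k if it is not.

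| k | Adverse-event criterion met | Adverse-event criterion failed |
|---|---|---|
| 0 | 1: not feasible | 0: not feasible |
| 1 | 2: not feasible | 1: not feasible |
| 2 | 3: with modifications | 2: not feasible |
| 3 | 4: with modifications | 3: with modifications |

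It decides the result only at k = 2, for example if consent fails while pooled retention and attendance pass. The documents report none of the three rates.

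**3. How much could incomplete capture matter?** This is an illustration only. Let p be the true per-participant probability of a related event and c the share of events captured; both are assumed. Then P(zero recorded) = (1 − p × c)^n. For p = 10%, n = 7, this is 0.90^7 = 0.48 at c = 1 and 0.95^7 = 0.70 at c = 0.5.

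| p (assumed) | n = 7, c = 1 | n = 7, c = 0.5 | n = 30, c = 1 | n = 30, c = 0.5 |
|---|---|---|---|---|
| 5% | 0.70 | 0.84 | 0.21 | 0.47 |
| 10% | 0.48 | 0.70 | 0.04 | 0.21 |
| 20% | 0.21 | 0.48 | 0.001 | 0.04 |

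Halving capture gives the same chance of a clean record as halving the true event rate.

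**The two thresholds side by side.** The Adverse events paragraph accepts no events of any kind, while Progression criteria item 1 counts only those related to the intervention treatment. The documents neither define an adverse event nor say who judges relatedness. The same injury could breach one rule and not the other.

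**The case against.** Several points on the other side are sound.

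- **Supervision.** With seven participants and a supervising researcher, a serious acute injury in a session is the event most likely to be seen. A reader might infer that the worse the injury, the less likely it is to be recorded. The documents do not support that general gradient; the gap is confined to injuries that emerge or worsen after the participant leaves.
- **Fitness tests.** A reader might also infer that injuries in the tests, such as the one in which participants "then produce a maximal 5 sec pull keeping the back from bending and arms straight", make the progression criterion falsely met. That does not follow from the criterion's wording. Pre-testing comes before randomisation (Experimental design), so an injury there cannot be related to the treatment, and a post-test injury arises from an assessment. The researcher also recorded the PACER in person. Test injuries matter only under the broader outcome threshold.
- **Silence is not absence.** Tracking of withdrawals may have included reasons, and the workout document, which is not reproduced, may have prompted for symptoms. But the plan specifies neither, and even a prompt on that document cannot reach someone who is absent.
- **The interview.** Its open questions, on what made attendance difficult and what was disliked, could well bring out an injury. This is a partial safeguard: it depends on accepting an invitation and does not feed the count.
- **Other signals.** An injury dropout lowers retention and attendance, so the rule is not wholly blind to it. Under per-trial scoring the dropout would show, although the injury would still be uncounted.

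**Conclusion.** The concern holds in a limited form. As written, the capture rule can miss a training-related injury that develops between sessions or after the last one in a participant who does not return, and the zero-event criterion would then be scored as met. This is a weakness of the method. It does not show that an event was missed or that the feasibility conclusion is wrong, because the documents give no adverse-event results and no consent, retention or attendance results.

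The effect on the decision is conditional. It needs an uncaptured related event and exactly two of the three rate criteria met; otherwise the category is the same either way. The claim that one dropout passes retention rests on pooled scoring of 7 randomised participants.

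Separately, the two adverse-event thresholds disagree. Reconciling them would settle whether test-session injuries count.

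**What to change.** **This study.** Data collection is complete, so only retrospective and reporting steps remain.

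1. Contact every randomised participant who missed sessions or stopped, and ask one standard question about pain, injury or illness since the previous contact.
2. Report the reason for each withdrawal.
3. Score the adverse-event criterion over all randomised participants. Where someone who stopped could not be asked, report it as *not confirmed* and do not score it as met.
4. State the capture window as a limitation.
5. Reconcile the Adverse events threshold with Progression criteria item 1: define an adverse event, say who judges relatedness, and say whether test-session events count.

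**Follow-on trial.** Ask the same question at every session, on return from any absence, at withdrawal, at both testing sessions and at the interview.

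**Cost.** A short contact per participant now, with some recall error because the question comes late. In the next trial, one line on forms already in use and a brief contact with anyone who stops. The adverse-event count may become less favourable.

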Seven healthy untrained adolescents ($16.9 \pm .7$ years old, 4 males and 3 females) from a northern Utah high school participated. The high school had 1,500 students across 10th, 11th and 12th grades. For the purpose of this study, untrained participants were defined as participants who reported being physically inactive with no regular participation in physical activity for the past month prior to the intervention. Participants were recruited through posted flyers and table events during lunch periods. Exclusion criteria included recent injuries or medical conditions that may influence high-intensity performance, currently enrolled in another training program including resistance, cardiovascular, or sports-based program, uninsured participants, drastically altering diet and use of performance-enhancing substances (i.e., creatine, pre-workout, post-workout supplements). Prior to the start of the study, participants and respective guardians read and signed informed consent, parent permission and assent documents. The 2023 PAR-Q + form and modified Copper Institute Fitnessgram and Activitygram questionnaires were used to screen participants.

Table 1. Summary Table of Participants

Category	Frequency	Percent
Sex		
Male	4	57%
Female	3	43%
Ethnicity		
Non-Hispanic	7	100%
Race		
White	7	100%

Category	Mean	Standard Deviation
Age	16.9	0.7
BMI	24.4	5.8
Body Fat Percentage	25.3	8.9

Table 1 shows the baseline participant characteristics.

Protocol

Participants performed 1-1 ½ hour sessions three times a week for four weeks under the supervision of the primary researcher. Participants followed the weekly progression adapted from Alcarez [32]. Exercises were adapted to fit the facility's equipment by prioritizing free weight compound movements over single joint machine exercises. In addition, instead of prescribing 6RM (85% of 1RM) to untrained participants, an autoregulatory approach using rate of perceived exertion (RPE) was prescribed (Figure 2). To simplify RPE use, participants used whole numbers such as 8 RPE which lowers the intensity from HRC's traditional intensity of 85% of 1RM to 80% 1RM. Literature supports the use of RPE-based loading as an effective alternative to prescribing percentages of 1RM for improving strength [39]. Use of RPE-based loading negated a safety concern with untrained participants conducting 1RM testing.

Figure 2. Equivalent Intensity Prescriptions of Traditional Percentage Based and RPE

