PACER. To assess cardiovascular fitness, the Progressive Aerobic Cardiovascular Endurance Run (PACER) assessment was used. Prior to the start of assessment, the primary investigator measured and marked a designated 20-meter distance in the gymnasium for testing. Participants were briefed on the assessment guidelines and participated in one practice opportunity prior to the official assessment. Once familiarized, participants ran the 20-meter distance in accordance to PACER cadences from the Cooper Institute for as long as possible. The test was terminated when the participant voluntarily stopped due to fatigue or when two laps were missed. The primary researcher recorded total number of successful levels. Once

completed, the primary researcher computed predicted peak VO₂ by using VO₂peak = 0.353(Laps) – 1.121(Age) + 45.619. This equation has been shown to have moderately strong linear relationships compared to measured VO₂ peak of adolescents [52].

Quantitative data analysis

Non-parametric analyses of primary and secondary outcomes were used due to the small sample size. Wilcoxon signed rank tests were used to test significance of pre and post-intervention data within treatment groups. Reports of Wilcoxon signed rank included medians, inner quartile ranges, z scores and p-values. Two sample Wilcoxon rank sum (Mann-Whitney) tests were used to test significance between treatment group differences. Reports of Wilcoxon rank-sum (Mann-Whitney) tests included medians, inner quartile ranges, U statistic and p-values. Due to an underpowered sample, effect sizes were calculated for all secondary outcome statistical tests. Given the exploratory nature of this study and the small sample, effect sizes may be more useful in guiding future research. Effect sizes were interpreted as small if $r = 0.2 - 0.5$, medium if $r = 0.5 - 0.8$ medium and large if $r > 0.8$. Statistical package STATA (version; BE 18.0, StataCorp, College Station, Texas, USA) was used and Alpha level was set at $P < 0.05$.

Qualitative assumptions

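### The labels for r (0.2/0.5/0.8) have no source and no formula behind them, and they call an expected 0.8 SD difference between arms 'small'

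*Combined protocol and SAP*

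**What the plan says.** In the combined protocol and SAP, section Quantitative data analysis, pre-post change is tested within arms: "Wilcoxon signed rank tests were used to test significance of pre and post-intervention data within treatment groups". The arms are then compared: "Two sample Wilcoxon rank sum (Mann-Whitney) tests were used to test significance between treatment group differences". The reporting list gives z scores for the signed-rank test and the U statistic for the rank-sum test.

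The same section adds: "Due to an underpowered sample, effect sizes were calculated for all secondary outcome statistical tests". The labelling rule follows: "Effect sizes were interpreted as small if $r = 0.2 - 0.5$, medium if $r = 0.5 - 0.8$ medium and large" when r is above 0.8. One scale therefore serves both tests. The section does not define r, say whether N counts participants or observations, or cite a source for the cut-offs. It gives these effect sizes a purpose: "effect sizes may be more useful in guiding future research".

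On size, the Sample size paragraph under Feasibility outcomes says: "A sample size of 30 participants per trial with 15 participants in each treatment group was established". The Participants section reports what was achieved: "Seven healthy untrained adolescents". The split of the seven by arm is not given.

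**The concern.** A standardised mean difference has no upper limit, whereas a correlation-type r cannot exceed 1. Cut-offs of 0.2, 0.5 and 0.8 are familiar on the first scale and mean something much more demanding on the second. If they are applied to r, a sizeable difference between the circuit and strength arms is described as small. The labels are the plan's only stated rule for interpreting effect sizes, and the plan offers effect sizes as a guide to later work. A later trial could be designed around a 'small' difference that is not small.

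A second problem follows from r being undefined. The attainable range of r depends on the formula and on the test, so the same word may be easy to earn for pre-post change and hard to earn for the randomised comparison.

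**Working it through.** **Inputs.** The cut-offs come from Quantitative data analysis, 15 per arm from Sample size, and the total of seven from Participants. Arm sizes at seven are my assumption: 3 v 4, with 2 v 5 as the alternative. The plan derives the cut-offs from nothing, so there is no figure of its own to reproduce.

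**1. The cut-offs on the d scale (equal arms).** d = 2r/√(1 − r²):
- r = 0.2: 0.4/√0.96 = 0.41
- r = 0.5: 1/√0.75 = 1.15
- r = 0.8: 1.6/√0.36 = 2.67

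In reverse, r = d/√(d² + 4) turns d = 0.2, 0.5 and 0.8 into r = 0.10, 0.24 and 0.37.

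**2. A true arm difference of 0.8 SD, normal data.** The chance that a member of one arm exceeds a member of the other is P = Φ(0.8/√2) = 0.714.
- Point-biserial: 0.8/√4.64 = 0.371
- Rank-sum z/√N, equal arms, large-sample value: √3 × (0.714 − 0.5) = 0.371
- Rank-biserial: 2 × 0.714 − 1 = 0.428

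All three lie in the 'small' band. Single trials vary. In 40,000 simulated 15 v 15 datasets with r = |z|/√N, the label was none in 15%, small in 64%, medium in 21% and large in 0.04%.

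**3. How far between-arm r can go if r = |z|/√N.** z = (U − n1n2/2)/√(n1n2(N + 1)/12), and the maximum is at U = 0:
- 15 v 15: 112.5/(√581.25 × √30) = 0.852. r > 0.8 needs U ≤ 6 of 225, so at least 1 − 6/225 = 97% of pairs favour one arm. In simulation a true 2 SD difference was 'large' in 15%.
- 3 v 4: 6/(√8 × √7) = 0.802 at complete separation. At U = 1 it is 5/7.483 = 0.668, so one discordant pair loses the label.
- 2 v 5: 5/(√6.667 × √7) = 0.732, so 'large' cannot occur.

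**4. The same question if r is rank-biserial.** The maximum is 1 at any arm sizes. r = 0.8 means P = 0.9, that is d = √2 × 1.2816 = 1.81. A true 2 SD difference at 15 v 15 was 'large' in 70% of simulations.

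**5. Within arms, signed-rank r = |z|/√n.** z = (W − n(n + 1)/4)/√(n(n + 1)(2n + 1)/24). When all participants change in the same direction (W = 0):
- n = 3: (3/√3.5)/√3 = 0.926
- n = 4: (5/√7.5)/√4 = 0.913

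The next values (W = 1) are 0.617 and 0.730. 'Large' therefore occurs exactly when everyone moves the same way. With no effect that has probability 2/2³ = 25% or 2/2⁴ = 12.5%. If the divisor is √(2n), the maxima fall to 0.655 and 0.645, and 'large' is impossible.

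**6. Chance labels under lower cut-offs, at the size studied.** Between arms at 3 v 4, U = 0, 1, 2, 3 arise in 1, 1, 2, 3 of the 35 orderings.
- r > 0.5 needs U ≤ 2 or its mirror image: 2 × 4/35 = 8/35 = 23%.
- r > 0.37 also admits U = 3 (3/7.483 = 0.401): 2 × 7/35 = 14/35 = 40%.
- The present r > 0.8 gives 2/35 = 5.7%.
- Within arms with z/√n, r > 0.5 occurs by chance in 4/8 = 50% (n = 3) and 6/16 = 37.5% (n = 4).

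**The case against.** The strongest reply is that verbal cut-offs are conventions. The documents do not say that these came from the d scale; the matching numbers only suggest it. A stricter scale is also arguably the cautious choice with seven participants, since lower cut-offs produce more impressive labels by chance. Both points stand. Neither answers the absence of a source and a formula, and the algebra in step 1 does not depend on where the numbers came from.

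A reader might infer that 'large' is almost unreachable throughout. The documents do not support that. The result belongs to the rank-sum test with |z|/√N, and the plan lists U rather than z for that test, so rank-biserial r is an equally open reading. Within arms with z/√n, 'large' comes easily at three or four participants.

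A reader might also infer that the labels are low by one or two classes. Against 0.1/0.3/0.5 they are low by at most one, apart from the exact boundary r = 0.5, which the plan's bands share. Values from 0.2 to 0.3 and above 0.8 keep their label. A two-class shift, from 'small' to 'large' for r between 0.37 and 0.5, appears only against the converted cut-offs.

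Nor does the plan dismiss p-values. It reports them with an alpha level and says only that effect sizes may be more useful.

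**Conclusion.** The point holds in a limited form. The cut-offs are unsourced, r is undefined, and on an r scale with equal arms the bands begin at 0.41, 1.15 and 2.67 SD. An expected 0.8 SD arm difference is labelled 'small' under all three common definitions of r, assuming normal data with equal spread. The labels are not comparable between the within-arm and between-arm tests. How hard 'large' is to reach depends on a formula that the plan does not give and, at seven participants, on arm sizes that it does not report.

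Severity is minor. The outcomes are secondary and exploratory, and the Sample size paragraph disclaims powered differences. None of the five items under Progression criteria uses an effect size, and no sample size or error rate changes.

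**What to change.** In Quantitative data analysis:

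- State the formula for r for each test, and whether N counts participants or observations.
- Replace the cut-offs with ones on the r scale: either the conversion 0.10/0.24/0.37 or the conventional 0.1/0.3/0.5. The choice matters. A 0.8 SD difference (r = 0.371) sits at the 'large' boundary under the first and is 'medium' under the second.
- Print the numeric r beside every label. For between-arm comparisons also print U/(n1 × n2), the share of pairs in which one named arm exceeds the other.
- If the stricter scale was deliberate, cite it and print the d equivalents 0.41/1.15/2.67.

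The cost is a short edit to the analysis text and relabelling of the results. The drawback is more 'large' labels by chance at the size studied. With a cut-off of 0.5 this is about 23% of 3 v 4 comparisons, and within arms 50% (n = 3) or 37.5% (n = 4). With the converted cut-off of 0.37 the 3 v 4 figure is 40%. No label should be read without its number.
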